6.3 Analysis Methods

The primary set of analyses will be related to the feasibility information on participant ‘flow’ and outcome data availability to inform the design of a future trial. Numbers of eligible participants, recruitment, and attrition rates will be compared with those of published studies in MND interventions, to evaluate if the MiNDToolkit was well accepted by families and professionals, and feasible for professionals. Formally, we will estimate, where possible, each rate with an associated 95% confidence interval. Of note, current published studies may not provide the ideal estimates for comparison to our proposed study, given the differences in the nature of the intervention. For this reason, we will have a cautious approach in the interpretation of attrition rates for the MiNDToolkit.

The distribution of each measure will be inspected to assess the possibility of ‘ceiling’ or ‘flooring’ effects, which would make an outcome inappropriate for a trial. The standard deviation, for Normally distributed variables, will be estimated with 95% confidence intervals, for use in future sample size calculations.

In addition, initial estimates of efficacy will also be provided. These will be estimated as between-group differences from a general linear model with appropriate link function and error distribution. Each model will include the baseline value of the outcome variable at baseline where available.

A number of individuals continued to access the online toolkit post the main follow-up time point and complete questionnaires. These will also be summarized but not included in any estimate of efficacy.

6.4 Missing Data and Invalid data

Trial questionnaires are completed online and a participant cannot ‘advance’ from one item until it is completed. However, it is possible for a participant to abandon entry online and not complete all questionnaires. The proportion doing this will be calculated together with a 95% confidence interval. Also, not all online entry was completed within the intended 30 days of six month follow-up. The number falling outside of 30 days will be calculated, again with a 95% confidence interval.

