#### Post-intervention assessment (within 1 month after the end of the intervention)

After the three-month intervention or usual treatment period, participants will be notified of the post-intervention assessment to complete via the platform.

Participants will be asked to complete the same assessments to that of the screening/pre-intervention assessment minus the socio-demographic, medical history questionnaires. In summary, the post-intervention assessment will include the following:

- About the person with MND: ALSFRS-R, MiND-B; FRS adapted, CSRI
- Carer questionnaires: PHQ-9, GAD-7, CES, ICECAP-A, CSRI, AAQ-II (six outcome measures being tested)

If post-intervention assessments are not completed after one week of the notification, a reminder will be sent. After a further week, participants will be contacted by telephone and given the option to complete the questionnaires over the phone with a researcher.

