## Stage 3: Opportunity for wait list controls to join the MiNDToolkit intervention platform

After the equivalent period of intervention (post-intervention assessment, 3 months), participants allocated to control will be given access to the MiNDToolkit Intervention Platform. This step had originally been suggested by the REC; given that now the intervention does not require intensive time from the HCP teams, we are able to offer this opportunity to all participants (See Fig 1). A post-intervention assessment will be issued following three months of using the toolkit, as per section f above.

The additional 3-month intervention and post-intervention assessment will also be made optionally available to participants originally randomised into the intervention group.

Monitoring and Semi-structured Interviews

1. Platform Monitoring

As shown in Figure 1, there will be continued monitoring of delivery of the MiNDToolkit to ensure its acceptability, feasibility and treatment fidelity. The following will be recorded:

- Numbers of potentially eligible participants
- Number of participants subsequently recruited into the study
- Number of withdrawals, and reason for withdrawal
- Use of the MiNDToolkit by carers: engagement with the platform, feedback on implementation and acceptability.
- Use of the MiNDToolkit by HCPs: frequency of use, duration/time taken.

These will be recorded through the MiNDToolkit platform. If HCPs or participants decide to continue accessing the platform after the end of the trial, these data relating to their use of the MiNDToolkit will continue to be collected. Access to the platform will be allowed for as long as there are adequate funding and resources to maintain the website, however data will only be collected for the purposes of analysis until the end of the ethical approval for the study.

2. Semi-Structured Interviews

In addition to platform monitoring, (1) HCPs will undergo a semi-structured interview on their utility and experience using the MiNDToolkit; (2) carers will be interviewed on their utility and experience using the MiNDToolkit, and in relation to barriers for implementation of strategies advised. The interviews will be optional for both HCPs and carers. As the MiNDToolkit is a new intervention we will be considering themes generated in the interviews and observations of delivery to inform minor edits of the MiNDToolkit and its online training for HCPs.

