## Appendix 1. Schedule of Assessment: MiNDToolkit Feasibility Study

|   | Consent +
Screening
measures | Baseline
measures | MiNDToolkit
Intervention
(0 – 3 months) | Post-
intervention
Assessment
(within 1 month | Second post-
intervention
assessment
(0-6 months)                                     |
|---|------------------------------------|----------------------|---|--|--|
|   | (0 months)                         | (0 months)           |   | after end of
intervention)                          | group
participants who
continue to use
modules or cross
over from control
group |
| Online session
length (minutes
approx.) | 15                                 | 30                   | 10 to 20                                      | 30   | 30   |
| Carers (about
MND patients)                |                                    |                      |   |  |  |
| MiND-B  | Ø                                  |                      |   | Ø  |  |
| ALSFRS-R                                      | Ø                                  |                      |   | Ø  | Ø  |
| FRS adapted                                   |                                    | M                    |   | R  | M  |
| CSRI adapted                                  |                                    | M                    |   | Ø  | M  |
| Socio-
demographic,
medical history     |                                    | Ŋ                    |   |  |  |
| Carers (self)                                 |                                    |                      |   |  |  |
| Informed Consent                              | Ŋ                                  |                      |   |  |  |
| Socio-
demographic,
medical history     | Ŋ                                  |                      |   | Ø  | ☑  |
| PHQ-9   |                                    | Ŋ                    |   | Q  | R  |
| GAD-7   |                                    | M                    |   | R  | M  |
| CES   |                                    | M                    |   | R  | M  |
| ICECAP-A                                      |                                    | Ŋ                    |   | Q  | Ø  |
| AAQ-II  |                                    |                      |   | Ø  | ☑  |
| Semi-structured
Interview                  |                                    |                      |   |  |  |

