3.5 Timing of outcome assessments

Assessments will be made at baseline prior to randomization and post intervention (within one month of the end of the intervention period of 3 months).

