6.2.2 Efficacy Outcomes

The following outcome efficacy variables, all related to the carer of the person with dementia, are collected within one month of the end of the intervention.

- Patient Health Questionnaire 9
- Generalized Anxiety Disorder Questionnaire 7
- Carer Experience Scale
- ICEpop CAPability measure for Adults

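### SAP 6.4 times late entry from a six-month follow-up that SAP 3.5 does not schedule; applied to the 3-month outcome, it would misclassify lateness

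*SAP*

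**What the plan says.** SAP 6.4, on missing and invalid data, states that "not all online entry was completed within the intended 30 days of six month follow-up". It then commits to a result: "The number falling outside of 30 days will be calculated, again with a 95% confidence interval".

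Elsewhere the timing is different and consistent:

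- SAP 3.5 lists two assessments only, baseline and "post intervention (within one month of the end of the intervention period of 3 months" (the parenthesis closes there).
- SAP 6.2.2 says the efficacy variables "are collected within one month of the end of the intervention".
- Protocol 2.5 heads the assessment "Post-intervention assessment (within 1 month after the end of the intervention") and applies it to both arms: "After the three-month intervention or usual treatment period, participants will be notified of the post-intervention assessment to complete via the platform".

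The protocol also has a later assessment. Stage 3 gives controls access to the toolkit after the 3-month point and says: "A post-intervention assessment will be issued following three months of using the toolkit". The intervention group may opt for a further three months and a further assessment. Appendix 1 shows this as "Second post- intervention assessment (0-6 months"), for those who continue or cross over. SAP 6.3 says that questionnaires completed after the main follow-up will be summarised but kept out of the efficacy estimates.

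**The concern.** The SAP's own schedule has no six-month follow-up, so the window in SAP 6.4 is tied to a date that does not belong to the main assessment. An analyst who programs the sentence as written would not be measuring timeliness of the 3-month outcome.

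This matters more here than it would in a confirmatory trial. SAP 6.2 defines no primary efficacy outcome, and SAP 6.3 makes participant flow and the availability of outcome data the primary set of analyses. How many carers complete the questionnaires on time belongs to that purpose, and SAP 6.4 plans to report it with a confidence interval.

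**Working it through.** **Inputs.** Intervention or control period of 3 months, then a one-month window (SAP 3.5, SAP 6.2.2, protocol 2.5). Window in SAP 6.4: 30 days, tied to six months. Sample size: up to 30 carers (SAP 3.3). Conversion used here: 1 month = 30.44 days.

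**Step 1: can the six-month figure be reproduced from the main schedule?**

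- End of the period: 3 × 30.44 = 91.3, about day 91.
- Close of the window: 91.3 + 30 = 121.3, about day 121.
- Six-month point: 6 × 30.44 = 182.6, about day 183.

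It cannot. The main assessment falls between months 3 and 4.

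**Step 2: can it be reproduced from Stage 3?** Three months as control (or on the first course) plus three months on the toolkit is 3 + 3 = 6 months from baseline, if the second period starts at month 3. This matches, so the second assessment is a possible source of the phrase.

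**Step 3: what happens if the six-month anchor is applied to the main outcome?** The phrase can be read in at least two ways.

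- As a deadline: 182.6 + 30 = 212.6, about day 213. The limit moves by 212.6 − 121.3 = 91.3 days, about three months.
- As a two-sided window: 182.6 − 30 = 152.6 to 212.6, about day 153 to day 213. This does not overlap day 91 to day 121. A window running only over the 30 days after month 6 does not overlap it either.

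| Completion day | SAP 3.5 (late after about day 121) | Six months + 30 days as deadline | Six months ± 30 days |
|---|---|---|---|
| 95 | on time | on time | out |
| 110 | on time | on time | out |
| 125 | late | on time | out |
| 160 | late | on time | in |
| 200 | late | on time | in |
| 220 | late | late | out |

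**Step 4: illustration.** The counts are assumed, since the documents give no completion dates. Take 30 entries, of which 6 arrive after day 121. Intervals are exact (Clopper-Pearson) 95%.

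- Rule of SAP 3.5: 6/30 = 20% late (7.7% to 38.6%).
- Deadline reading, if all 6 arrive before day 213: 0/30 = 0% (0% to 11.6%).
- Two-sided reading, if all 30 arrive before day 153: 30/30 = 100% out of window (88.4% to 100%).

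The same data could therefore be reported as 0%, 20% or 100%. The direction of the error depends on the reading.

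**The case against.** The strongest reply is that SAP 6.4 may mean the Stage 3 assessment. The protocol does have an assessment at about six months, and the last paragraph of SAP 6.3, shortly before, describes people who went on using the toolkit and completed later questionnaires. Stage 3 also refers back to the earlier assessment procedure, which may carry the 30-day window over. On that reading the six-month anchor is right. This stands as a possibility, but it does not rescue the text. SAP 6.4 does not name that assessment, SAP 3.5 does not schedule it, and the only assessment used to compare the arms would be left without a timeliness measure.

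A second reply is that the six months is a slip for three. The sentence that commits to the calculation mentions only 30 days, which agrees with the one-month window elsewhere, and staff may already count from month 3. The result would then be correct despite the wording. That is also possible, but it means relying on the analyst to depart from the SAP.

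A reader might go further and infer three things that the documents do not support:

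- That the reported proportion is bound to be wrong. This follows only if the six-month anchor is applied to the main outcome.
- That the efficacy estimates are affected. The SAP has no rule excluding late entries from the models, so the lateness definition does not change who is analysed.
- That this count fixes the visit window or reminder schedule of a future trial. Neither document says so, and late entry is not among the feasibility outcomes listed in SAP 6.2.1; it appears only in SAP 6.4.

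**Conclusion.** SAP 6.4 contradicts SAP 3.5, SAP 6.2.2 and protocol 2.5 on the time point from which late entry is judged, and it does not say which assessment it means. Both ways of resolving it require a change. Either the anchor is wrong for the main outcome, or the main outcome has no timeliness measure.

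If applied to the main outcome, the anchor shifts the lateness limit by about 91 days under the deadline reading, or puts every on-time entry out of window under the two-sided reading. The day counts rest on 30.44 days per month, and the percentages in the illustration rest on assumed counts. The actual number misclassified cannot be computed from the documents.

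The mismatch itself is certain; its consequence depends on how the sentence is applied. The effect is limited to one descriptive feasibility result, in a study whose main analyses concern feasibility. The efficacy estimates do not change.

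**What to change.** Rewrite the last two sentences of SAP 6.4 so that they:

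- name the main post-intervention assessment;
- count entries completed more than 30 days after the end of the 3-month intervention or control period, as a one-sided limit;
- report the number, the proportion and its 95% confidence interval.

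The SAP should also say which recorded date marks the end of that period. The protocol mentions both the end of the period and a notification to complete the assessment, and the documents do not settle which one starts the clock.

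If timeliness of the second assessment, at about six months, is also of interest, report it separately against its own due date.

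The cost is one rewritten statement in the SAP and one derived variable. No extra data collection should be needed if the platform holds the completion dates that SAP 6.4 already relies on.

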6.5 Additional analyses

Currently no additional subgroup or sensitivity analyses are planned.

6.5 Software

Statistical analyses will be carried out using SAS version 9.4.

